6.2 Intent-to-treat incidence rate ratios comparing product use groups to the control group

IRRs with 95% confidence intervals will be calculated comparing each product use group (groups 2-4) to the control group (group 1) using the IR function in STATA. In addition, IRRs with 95% confidence intervals will be calculated comparing each vaginal probiotic group (group 3 and 4) to the metronidazole group (group 2). As before, these IRRs will be calculated for each primary efficacy outcome and for each of the three time periods: between the Enrolment visit and the M2 visit (during product use), between the M2 visit and M6 visit (after cessation of product use) and for the entire study period after randomisation. They will be reported in the following table (one table for each time period):

	Group 2 vs 1 IRR (95% CI)	Group 3 vs 1 IRR (95% CI)	Group 4 vs 1 IRR (95% CI)	Group 3 vs 2 IRR (95% CI)	Group 4 vs 2 IRR (95% CI)
Incident BV by					
modified Amsel					
criteria					
Incident Nugent 4-10					
Incident Nugent 7-10					
Incident TV by culture					
Incident symptomatic					
vaginal candidiasis					

6.3 Per protocol incidence rate ratios comparing product use groups to the control group

A few significant protocol deviations occurred that could have an impact on the primary analysis results:

- CT/NG PCR testing was not available at the RU clinic and was outsourced to the National Reference Laboratory in Kigali, Rwanda. Test results were usually available only weeks after sample collection. We realised that this might be an issue early on and increased the sample size of each randomisation group to 17 instead of 15 to allow for exclusion of women who were randomised while having an ongoing CT or NG infection. Unfortunately, the number of women with a CT or NG infection in each randomisation group turned out to be higher than expected: 8/17 in Group 1, 7/17 in Group 2, 4/17 in Group 3, and 7/17 in Group 4 (Fisher's exact p = 0.53).
- Discrepancy between modified Amsel criteria and Nugent score at the Enrolment visit: Women could be enrolled if they had negative modified Amsel criteria after having completed the 7-day metronidazole treatment. Nugent scores became available later. In a handful of cases, women who were randomised because they no longer had BV by modified Amsel criteria turned out the have a Nugent score of 7-10 at the Enrolment visit.

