- 3. Another special case is the use of antibiotics and/or antifungals during follow-up. If these were prescribed by the study physician due to symptomatic BV, TV, or symptomatic vaginal candidiasis, their use is causally related to the primary endpoints. These women will therefore be included in the per protocol analyses. However, if women used antibiotics and/or antifungals extensively during follow-up, including for reasons not related to the primary endpoints, they may be excluded in the per protocol analyses. This will be determined on a case-by-case basis by the Chief Investigator and each case will be described.

The analyses described in 6.1 and 6.2 will be repeated after exclusion of the participants described in 1, 2, and 3 above. If additional significant protocol deviations are discovered during data analyses (which is unlikely), additional exclusions might be made. These will also be determined on a case-by-case basis and each case will be described.

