6.4 Adjustment for confounding: generalised estimating equation (GEE) models

Other behavioural and clinical characteristics might also influence the primary efficacy outcomes. Some of these variables were collected at baseline but also at the M2 and M6 visits.

Sexual behaviour	Baseline	M2	M6	p-value ²
Number of sex partners in last month at baseline or per				
month during follow-up period (median, IQR)				
Currently has a main sex partner (n %) ¹				
Obtained a new main partner during period (n %)	NA			
Lives together with main sex partner (n %)				
Main sex partner circumcised (n % per category)				
- Yes				
- Does not know				
- No				

We will assess any behavioural changes over time in the total study population as follows:

Main sex partner has other sex partners (n % per category)				
- Yes				
- Does not know				
- No				
Vaginal sex frequency last 2 weeks (median, IQR)				
Any condom use in past two weeks (n %)				
Exchanged sex for money/goods in past month (n %)				
Contraceptive practices, vaginal practices, menses	Baseline	M2	M6	p-value ²
Currently using a modern method of contraception other				
than condoms (n % per category):				
- Pills				
- Injections				
- Implant				
- Copper IUD				
- Sterilised				
- Other				
Weekly frequency of vaginal practices since the last visit				
(includes water only using fingers, water and soap using				
fingers, paper/cloth/cotton wool with or without liquid, and				
traditional herbs, stones, or powders)				
Amenorrhea due to hormonal contraception (n %)				
Amenorrhea due to other reason (n %)				
If no amenorrhea, duration of bleeding (median, IQR)				
If no amenorrhea, any vaginal sex during menses (n %)				

1. If missing values, a footnote detailing the number of missing values for a particular variable will be added to the table.

2. McNemar's test for binary or categorical variables and Wilcoxon test for medians.

We will use generalised estimating equation (GEE) models with Nugent 4-10 (compared to Nugent 0-3) at any study visit after randomisation as the outcome and randomisation group as the main predictor (and indicator variable with Group 1 as the reference group) to adjust for the potential effects of these characteristics. A similar model will be run with Nugent 7-10 (compared to Nugent 0-6) as the outcome.

Assessment for effect modification:

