We will assess CT and NG infection at Screening (combined variable: one or both infections diagnosed by PCR at Screening and not treated until later on in the study) for effect modification. If statistically significant effect modification is present, the relevant women will be excluded from the GEE models. If no effect modification is present, the presence of CT and/or NG infection will be adjusted for (see below). We expect the number of women with a Nugent score of 7-10 at the Enrolment visit, or who used antibiotics and/or antifungals extensively, to be too small to assess for effect modification or confounding.

Adjustment for confounding:

Since the sample size of the Rwanda VMB Study is small, we do not have sufficient statistical power to adjust for many confounding variables. We will focus on two variables: CT/NG infection (see above) and study product adherence (see below). However, if we find that any of the variables in the tables in sections 4.2 and 4.3 and in the table are imbalanced between the randomisation groups, or if any behaviours changed significantly over time (see table above), one or two additional variables may be added to the models.

Adherence: Adherence to the study interventions was assessed at the D7, M1 and M2 visits by structured interviewer-administered questionnaire, review of a diary card that the participant completed in between

study visits, review of returned used packaging and unused product, and by asking the participant to complete a self-rating adherence scale. These different sources of adherence data will be triangulated to arrive at an overall level of adherence (between 0-100%) for each participant between the Enrolment and D7 visits, D7 and M1 visits, M1 and M2 visits, and the Enrolment and M2 visits. Women were allowed to cease product use during menstrual bleeding and these days will therefore not be taken into account. Adherence will be plotted in a line graph for randomisation groups 2, 3 and 4 with study visits (D7, M1, and M2) on the horizontal axis and the adherence percentage on the vertical axis. In the GEE models, only one overall adherence measure (% between the Enrolment and M2 visits) will be used, with the adherence level for women in Group 1 (who did not use any study product) set at 100%.

7. Analysis of follow-up data: primary safety outcomes

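### SAP 6.4 lets a low-powered interaction test decide whether up to 26 of 68 women stay in the adjusted Nugent GEE models

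*SAP*

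**What the plan says.** SAP 6.4 fits GEE models with Nugent 4-10 at any post-randomisation visit as the outcome and randomisation group as the main predictor, and adds a second model: "A similar model will be run with Nugent 7-10 (compared to Nugent 0-6) as the outcome". The candidate modifier combines CT and NG: "one or both infections diagnosed by PCR at Screening and not treated until later on in the study". The rule has two branches. On one, "If statistically significant effect modification is present, the relevant women will be excluded from the GEE models". On the other, "If no effect modification is present, the presence of CT and/or NG infection will be adjusted for". The form of the test, its scale and its significance level are not given; elsewhere in the SAP, 0.05 appears only as a trigger for follow-up Fisher comparisons (sections 5 and 7.3). Nor does the SAP say whether one decision covers both Nugent models.

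SAP 6.3 gives the infected women per group: "8/17 in Group 1, 7/17 in Group 2, 4/17 in Group 3, and 7/17 in Group 4". It also removes them from the per-protocol rate ratios by a fixed rule: "The analyses described in 6.1 and 6.2 will be repeated after exclusion of the participants described in 1, 2, and 3 above". Protocol 5.2 foresaw that such women's data might be dropped from some analyses, without naming which or on what trigger.

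**The concern.** A p-value computed from the outcome data selects the population for the SAP's only covariate-adjusted comparison of groups. The two branches estimate different things: the effect in uninfected women, or the effect in all randomised women. This causes three problems.

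- If modification is real, the useful output is an estimate in each stratum. The rule instead drops from the GEE the stratum in which the effect differs.
- If the test is not significant, the SAP reads that as absence of modification. With so few infected women per group, non-significance says little.
- If the test fires by chance, the infected women are dropped in exactly those trials where the estimates in uninfected women have drifted away from those in infected women. The intervals from the reduced model then ignore that selection.

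The pilot's data are meant to help choose interventions for a later efficacy trial (Protocol 3.2), so a population selected by chance could mislead that choice.

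**Working it through.** **1. The plan's own figure.** SAP 6.3 reports Fisher's exact p = 0.53 for CT/NG across the groups. Full enumeration of the 2x4 table gives 0.544 (Pearson: chi-square = 9/6.5 + 9/10.5 = 2.24, p = 0.524). The small mismatch does not matter here, because both show no clear imbalance.

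**2. Women at stake.** 8 + 7 + 4 + 7 = 26 of 68 (38%). Exclusion leaves 9, 10, 13 and 10, or 42. This takes every case counted in SAP 6.3 to meet the definition in 6.4, which is an inference.

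**3. Loss of precision.** If the variance goes as 1/n per group, the SE ratio for Group 2 or 4 versus Group 1 is √[(1/9 + 1/10)/(2/17)] = 1.34, and for Group 3 versus Group 1 it is √[(1/9 + 1/13)/(2/17)] = 1.26. The simulated GEE gives 1.27-1.39 (about 1.3 with no modification).

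**4. Power of one interaction contrast.** Illustrative inputs come from Protocol 3.1: about 50% recurrence, and a 57% reduction, so 0.50 × 0.43 = 0.215 in uninfected women and no reduction in infected women. Using these as per-visit Nugent rates is an assumption. With four visits and within-woman correlation ρ:

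- Difference in log odds ratios: logit(0.50) − logit(0.215) = 1.295.
- Variance = [(1 + 3ρ)/4] × Σ 1/[n p(1 − p)].
- Group 2 versus 1, ρ = 0.5: 0.625 × (1/2.25 + 1/1.688 + 1/2.00 + 1/1.75) = 0.625 × 2.108 = 1.318, so SE = 1.148.
- Power ≈ Φ(1.295/1.148 − 1.96) = 0.20.

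For ρ from 0.3 to 1.0 the power is 0.25 down to 0.13 across the three products.

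**5. Simulation of the whole rule.** 4,000 trials per scenario.

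- From the SAP: 17 women per group, the CT/NG counts above, and attendance of 66, 67, 66 and 64 at the four visits (SAP 3.1).
- Assumed: control positivity of 30-50% per visit; random-intercept SD 0.5-2; visits missing at random; exchangeable logistic GEE; 3-df Wald test at 0.05.
- Run with and without an adherence covariate, because SAP 6.4 states: "In the GEE models, only one overall adherence measure (% between the Enrolment and M2 visits) will be used". Assumed adherence averages 80% in Groups 2-4 and has no effect on the outcome.
- Trials with an all-0 or all-1 CT/NG-by-group cell (0-13%) were set aside.

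| Quantity | Robust SE | Small-sample-corrected SE |
|---|---|---|
| No modification: joint test fires | 7-12% | 2-5% |
| No modification: any single term significant | 16-20% | not run |
| OR 0.3 uninfected, 1 infected: joint test fires | 15-40% | 6-25% |
| Same: any single term significant | 29-61% | not run |
| No effect at all: at least one of three 95% CIs excludes 1, fixed 68 women | 14-17% | 9-12% |
| Same, fixed 42 women | 15-18% | 8-12% |
| Same, 42 women, given that the joint test fired | 27-46% | 25-43% |
| Same, whole rule minus fixed 68-woman model | +1 to +3 points | +0.5 to +1.3 points |

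The conditional row rests on about 360-480 fired trials per scenario (robust) or 130-180 (corrected, Monte Carlo SE about 4 points). A simpler simulation, with complete visits and no adherence covariate, agrees: the joint test fires in 8.5-11.6% with no modification and in 16-41% when the effect vanishes in infected women.

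**The case against.** The case for leaving the rule alone has real substance.

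- **Exclusion has a design basis.** Freedom from CT and NG was an eligibility condition (Protocol 5.2), and groups were enlarged to 17 so that such women could be excluded (SAP 6.3). Infection was measured before randomisation, so dropping these women does not select on a post-randomisation event. This stands: excluding them is legitimate if fixed in advance. It does not justify letting the outcome data decide.
- **Other analyses show both populations.** The intent-to-treat ratios keep everyone and the per-protocol ratios always drop these women. This stands and confines the damage to the GEE. The per-protocol set also drops women for other reasons, so it reveals modification only in part.
- **The average cost is small.** With no modification, 88-93% of trials end in the all-women model that is recommended below, and overall error rises by only 1-3 points. This stands. The harm lies in the trial where the rule fires, and in false reassurance where it does not.
- **Power depends on the form of the test.** If any single significant term counts, detection reaches 61%. That reading also raises chance exclusion to 16-20%.
- **The subgroups the SAP sets aside are smaller.** It expects women with Nugent 7-10 at Enrolment or extensive antibiotic or antifungal use "to be too small to assess for effect modification or confounding". CT/NG covers 26 women, so treating it differently is not an inconsistency. The interaction still rests on 4 to 8 infected women per group.
- **It is a pilot without a sample-size calculation.** True, and a reason not to hang a population choice on a significance test.

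**Conclusion.** The concern holds. The joint test misses modification in 60-85% of trials even when an odds ratio of 0.3 disappears completely in infected women, so a non-significant result cannot be read as no modification. When the test fires by chance, the 42-woman model is about twice as likely to show a false product-versus-control difference as the same model fixed in advance, and more than twice with the small-sample correction.

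The effect is limited to the adjusted GEE models and is small on average. The point should be corrected, but it does not undermine the intent-to-treat or per-protocol results. The size figures depend on the assumed event rates, correlation, adherence distribution, form of test and 0.05 level, because the documents give none of these for this test. The existence of the rule and the 26-of-68 count do not depend on them, except that the count takes all SAP 6.3 cases to meet the 6.4 definition.

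**What to change.** Delete the test-and-exclude rule from SAP 6.4 and replace it with:

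- Both Nugent GEE models include all 68 randomised women, with CT/NG at Screening as a pre-specified covariate.
- The same models are run in CT/NG-negative women only, as a sensitivity analysis for both outcomes, whatever any interaction test shows.
- The group-by-CT/NG interaction is reported with confidence intervals as descriptive, where estimable, with no decision attached to its p-value.

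Making the 42 uninfected women the main GEE set would also remove the fault if fixed in advance, but it answers a different question and loses precision.

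The cost is a wording change and one extra model per Nugent outcome, with no new data. Interaction and stratum estimates resting on 4-8 infected women per group will be very wide and may not always be estimable; the SAP should say so.

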1.1 Study overview

A flow diagram of study visits, and numbers of women seen at each visit, is shown in Figure 1. Women at high risk for HIV, sexually transmitted infections (STIs), and BV were targeted using community mobilisers who were high risk women themselves. Women who were potentially eligible (HIV-negative, non-pregnant, aged 18-45, and sexually active with high risk of HIV/STI/BV) and interested in participating were invited to visit the RU clinic for screening procedures. Please refer to the study protocol for a full listing of eligibility criteria. At the screening visit, a face-to-face interview, speculum examination, and testing for HIV, pregnancy, urinary tract infection (UTI), BV (by Amsel criteria and Nugent scoring), and *Trichomonas vaginalis* (TV; by wet mount and InPouch culture) were conducted. At the end of the visit, preliminary eligibility was assessed, and initial treatments and referrals were given based on available test results. Additional STI testing was conducted on stored samples after the participant had left the clinic. Results of those tests were given as required, and eligibility was reassessed. At the end of the Screening and Results Visits cascade, women were either declared ineligible or diagnosed with BV by Nugent score and/or TV on wet mount or by culture and treated with 500mg oral metronidazole twice per day for 7 days.

At the Enrolment Visit, only women whose BV/TV treatment had been successful (no BV by Amsel criteria and no TV on wet mount), who were still not pregnant, and who were free of STIs and UTI, were randomised to 4 groups as follows:

Group 1) Behavioural 'vaginal practices cessation and safer sex' counselling only (also referred to as the 'control group');

Group 2) Behavioural counselling plus oral metronidazole 500mg, twice per week for two months; Group 3) Behavioural counselling plus Ecologic Femi vaginal capsule, once per day for 5 days immediately after oral metronidazole treatment followed by thrice weekly for two month;

Group 4) Behavioural counselling plus Gynophilus vaginal tablet, once every 4 days for two months. Participants took/inserted the first dose of their intervention (if applicable) under direct observation at the Enrolment Visit.

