4.3 Other baseline characteristics by randomisation group (collected at Enrolment)

Vaginal practices	Group 1 N=17	Group 2 N=17	Group 3 N=17	Group 4 N=17	Total N=68
Weekly frequency of washing body (median, IQR)					
Ever washing the genitalia, and if yes, location of					
washing (n % per category) ¹					
- Yes, outside only					
- Yes, both inside and outside					
- Yes, inside only					
- No					
Weekly frequency of cleaning inside the vagina					
(median, IQR)					
Timing of cleaning inside the vagina (n % per category) ²					
- Before sex					
- After sex					
- While bathing					
- During/after menses					
- Other (described in a footnote)					
Vaginal practices in the past 12 months, other than					
vaginal practices to manage menses (n % per category) ²					
- Water only using fingers					
 Water and soap using fingers 					
 Water with paper/cloth/cotton wool 					
 Water and soap with paper/cloth/cotton wool 					
 Paper, cloth, cotton, wool without liquid 					
- Traditional herbs, stones, or powder					
- Western vaginal medicine					
 Other (described in a footnote) 					
- No vaginal practices					
Practices to manage menstrual blood or spotting in the					
past 12 months (n % per category) ²					
- Tissue, toilet paper, paper, cloth or cotton wool put					
inside the vagina					
- Tissue, toilet paper, paper, cloth or cotton wool					
placed in underwear					
- Sanitary pad					
- Tampon					
 Water, without soap, inside the vagina 					
 Water, with soap, inside the vagina 					

- Other (describe in a footnote)					
- Nothing was used					
- Did not have menses in past 12 months					
Used anything inside the vagina other than plain water					
in the last two weeks (n/N %)					
If yes, what was used (n/N % per category) ¹					
- Soap					
- Soap - Paper/cloth/cotton wool					
- Tampon					
- Traditional herbs, stones or powders					
- Western vaginal medicine					
- Other (described in a footnote)					
	Group 1	Group 2	Group 3	Group 4	Total
Menses	N=17	N=17	N=17	N=17	N=68
Regular menstrual cycle (n % per category)					
- Yes					
- No, irregular					
- Amenorrhea due to hormonal contraception					
- Amenorrhea due to other reason (described in a					
footnote)					
Duration of bleeding(median, IQR)					
Amount of bleeding (n % per category)					
- Light					
- Moderate					
- Heavy					
History of painful periods (n %)					
Self-reported vaginal sex during menses in the past 12					
months (n %)					

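### The SAP 6.4 GEE models do not adjust for the Enrolment Nugent score, and the SAP's optional-covariate rule cannot bring it in

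*SAP*

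**What the plan says.** SAP 6.4 fits GEE "models with Nugent 4-10 (compared to Nugent 0-3) at any study visit after randomisation as the outcome", with randomisation group as main predictor and Group 1 as reference. A second model uses 7-10 against 0-6. On adjustment it says "We will focus on two variables: CT/NG infection (see above) and study product adherence (see below"). One or two further variables may be added if "any of the variables in the tables in sections 4.2 and 4.3 and in the table are imbalanced between the randomisation groups", or if behaviours changed over time.

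Enrolment Nugent is mentioned once in 6.4: "We expect the number of women with a Nugent score of 7-10 at the Enrolment visit, or who used antibiotics and/or antifungals extensively" is expected to be too small to assess for effect modification or confounding.

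On entry, SAP 1.1 randomised "only women whose BV/TV treatment had been successful (no BV by Amsel criteria and no TV on wet mount"). Nugent did not decide entry. SAP 6.3 reports that the scores arrived later and that a handful of randomised women "turned out the have a Nugent score of 7-10 at the Enrolment visit". It gives no count, no split by arm, and nothing on 4-6.

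The score itself was scheduled for every woman at Enrolment (Protocol 6.4 and 15.2; SAP Table 1), and SAP 5 states that all women were Nugent-scored at all visits.

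**The concern.** The GEE outcome is the Nugent state at a visit, not a new episode. A woman who enters at 4-10 and stays there counts as positive at every follow-up visit, whatever her product does. Her score at randomisation is the baseline value of the outcome and an obvious candidate predictor. With arms of 17, a few more abnormal women in one arm by chance can look like a product effect or hide one. Protocol 3.2 says these data will be used to choose interventions for the efficacy trial. SAP 8.1 already takes Enrolment data, where available, as baseline for the secondary outcomes; 6.4 does not do so for its own outcome.

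**Working it through.** **1. Can the plan's own rules bring the score in?**

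- The reason given in 6.4 concerns women at 7-10. Women at 4-6 are positive on the first GEE outcome and are not mentioned. A 0-10 covariate does not depend on how many women are at 7-10.
- The optional-covariate rule draws on three tables. Table 4.2 has Nugent rows, but from Screening, before the metronidazole course. Table 4.3, "Other baseline characteristics by randomisation group (collected at Enrolment"), lists vaginal practices, menses and probiotics, with no Nugent row. The 6.4 table lists behaviours. An imbalance in Enrolment Nugent therefore cannot trigger the rule.
- By arm, the score appears at most in the 6.1 line graph of medians. The median of 17 is the 9th ordered value, so up to 8 women can be at 4-10 while it stays at 0-3.
- SAP 3.2, 7.1 and 7.2 were not available for this check.

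**2. How often would arms be imbalanced?** The plan gives no figure to reproduce. Take the numbers at 4-10 in control (X) and in a product arm (Y) as independent Binomial(17, p), with p assumed. The columns are P(X − Y ≥ 4), P(|X − Y| ≥ 4), and, for any of three product arms, Σ P(X = c)·[1 − P(|Y − c| < 4)³].

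| p (assumed) | Control worse by ≥4 | Either direction | Any of three arms |
|---|---|---|---|
| 10% | 2.2% | 4.4% | 10.8% |
| 20% | 6.5% | 13.0% | 29.8% |
| 30% | 9.4% | 18.9% | 41.1% |
| 40% | 11.0% | 22.0% | 46.8% |

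**3. What does such an imbalance do?** A hand example with no product effect: 8/17 abnormal in control, 4/17 in a product arm, later risk 0.7 if abnormal at Enrolment and 0.3 if not (all assumed).

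- Control: (8 × 0.7 + 9 × 0.3)/17 = 8.3/17 = 0.488.
- Product: (4 × 0.7 + 13 × 0.3)/17 = 6.7/17 = 0.394.
- OR = (0.394/0.606)/(0.488/0.512) = 0.68.

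**4. Simulation of the 6.4 model.**

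- From the SAP: 4 arms of 17, 4 follow-up visits, CT/NG in 8, 7, 4 and 7 of 17.
- Assumed: all visits attended; control prevalence per visit 45% (4-10) and 25% (7-10); between-woman SD 1.5 on the logit scale; 6-7% at 7-10 at Enrolment; product-arm adherence averaging 85% and unrelated to outcome; correlation 0.2, 0.4 or 0.6 between Enrolment score and later BV tendency.
- Method: logistic GEE with robust SE; 12,000 null trials and 8,000 with conditional OR 0.3 per scenario.

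Nugent 4-10, no product effect, control worse by 4 or more (false benefit at nominal 2.5%):

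| Correlation | Median OR without score | False benefit without score |
|---|---|---|
| 0.2 | 0.90-0.91 | 4-5% |
| 0.4 | 0.78-0.82 | 6-7% |
| 0.6 | 0.70-0.75 | 8-10% |

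With the score added, the median OR is 0.99-1.08 and false benefit 2.5-4%. For 7-10 the median OR is 0.90-0.93, 0.79-0.83 and 0.69-0.72 without the score, against 1.00-1.10 with it.

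With a true conditional OR of 0.3 and the product arm worse by 4 or more, benefit on 4-10 is detected in 26-28%, 21-24% and 16-18% without the score, and in 34-37%, 35-40% and 40-43% with it.

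**5. Over all trials.** A separate run (4,000 null trials per scenario, p = 10% and 30%) shows the mirror image. When control is better by 4 or more, false benefit is 0-1.8% without the score and 2.5-8.0% with it. Over all trials it is 3.0-3.4% without and 3.1-3.5% with. The SD of the log OR is 0.57-0.59 without and 0.58-0.59 with. Two-sided type I error is 6-7% either way. Overall power for 4-10 rises from 33-34% by about 1, 3 and 6-7 points, and for 7-10 from 27-29% by about 0.5, 2 and 3-4 points.

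**The case against.** The SAP's authors considered Enrolment Nugent, gave a reason, and kept the model small because power to adjust is limited. That is a defensible stance in a 68-woman pilot with no formal sample size, so this is a judgement and should not be read as an oversight. What remains is that the reason does not extend to 4-6 or to the 0-10 score.

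A reader might infer that all the efficacy results carry this problem. The documents do not support that. SAP 6.1 counts a Nugent 4-10 case as incident only after 0-3 at the previous visit or after adequately treated symptomatic BV, and it separates persistent from incident infections. SAP 6.3 adds that "The analyses described in 6.1 and 6.2 will be repeated after exclusion of the participants described in 1, 2, and 3 above", which removes women at 7-10 at Enrolment. So 6.1-6.2 largely deal with persistence. The 6.3 exclusion does not name 6.4 and leaves women at 4-6 in.

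The sizes above rest on inputs the documents do not give; the only fact is a handful at 7-10. The larger shifts need both an unlucky allocation and a correlation of 0.4-0.6. Missed visits were not simulated, nor was the 6.4 variant that drops women with CT/NG.

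**Conclusion.** The point holds as a minor improvement, mainly confined to 6.4. The models leave out a baseline value of their own outcome that was scheduled for everyone, and no rule or table in the available text lets it back in.

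A reader might go further and infer systematic confounding, inflated type I error or lost precision. None of these follows. Allocation was random, so the issue is chance imbalance. False benefit over all trials is about 3% with or without the score, with no net excess, and the SD of the log OR is essentially the same. The gain is a fairer estimate in the trials that happen to be imbalanced: a median null OR for 4-10 of about 1.0-1.1 instead of about 0.7-0.9 when control is worse by four or more women. Overall power may also rise by about 1-7 points for 4-10 and somewhat less for 7-10. If the score predicts little, the benefit is close to nil.

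**What to change.** 1. Add to SAP 6.4: both GEE models will include the Enrolment Nugent score (0-10) as a pre-specified covariate. For the 4-10 model, a sensitivity analysis will use 0-3 versus 4-10 instead. If the 7-10 model does not converge, it will be reported without the score and labelled as such.
2. Add Enrolment Nugent 0-3 / 4-6 / 7-10 by arm to Table 4.3. This is useful even if the sponsor prefers to leave the models as they are.

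The cost is a short addition to 6.4 and one block of rows, using data already scheduled. The downside is one more parameter in a small model and an assumed linear effect. That costs most if effect modification leads to exclusion of women with CT/NG: 8 + 7 + 4 + 7 = 26 of 68, leaving 42. In the simulation of all 68 women, the 0-10 score did not make fitting fail more often (0-0.6% with or without it). The two-category version failed in up to 4.3% of trials at 10% prevalence, which is why it is only the sensitivity analysis.

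### The adjusted GEE treats post-randomisation product adherence as a confounder and fixes all controls at 100%, so its group coefficients no longer estimate the effect of randomised assignment

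*SAP*

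**What the plan says.** SAP 6.4 fits GEE models for Nugent 4-10, and again for Nugent 7-10, "at any study visit after randomisation as the outcome and randomisation group as the main predictor", with Group 1 as the reference. Under its confounding heading it limits adjustment mainly to two covariates: CT/NG infection at Screening and study product adherence.

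On timing, "Adherence to the study interventions was assessed at the D7, M1 and M2 visits". Several sources are combined "to arrive at an overall level of adherence (between 0-100%) for each participant". In the GEE, "only one overall adherence measure (% between the Enrolment and M2 visits) will be used". Since controls have no product to adhere to, the SAP assigns them a value: the model is to be run "with the adherence level for women in Group 1 (who did not use any study product) set at 100" per cent.

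The section allows one or two further variables if they are imbalanced between groups or if behaviour changes over time. It does not declare a full-adherence estimand, does not include a group-by-adherence term, and does not commit to a GEE without adherence. The intent-to-treat incidence rates and rate ratios in SAP 6.1 and 6.2 do not use adherence.

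**The concern.** A confounder of a randomised comparison would have to precede assignment. Product adherence follows assignment, and in the control group it does not exist. Giving controls a value does not make it a shared baseline characteristic. It only decides at which point on the adherence scale the product groups are compared with controls.

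That comparison sets a hypothetical 100%-adherent product user against every control, whatever her own disposition to adhere. If women who adhere well have a lower underlying BV risk, an inert product looks beneficial; if they have a higher risk, it looks harmful.

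The timing adds to the problem. Outcomes at D7 and M1 are modelled with an adherence figure that runs to M2. Part of the covariate therefore follows the outcome it is meant to explain and may respond to it.

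The 100% value also sits awkwardly with Protocol 4.2. Feasibility objective 2 treats adherence to all four interventions, including the control counselling, as an open question.

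These are the only adjusted efficacy models in a pilot meant to help choose interventions for a later trial. They could disagree with the intent-to-treat rate ratios for reasons unrelated to the products.

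**Working it through.** The plan gives no estimate, power or sample size for the GEE, so there is no figure to reproduce.

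**Inputs from the documents.** 17 women per group, 68 in total (SAP 4.2, 6.3); four post-randomisation visits (D7, M1, M2, M6); controls coded 100; adherence on a 0-100% scale. Linear entry of adherence is implied by SAP 6.4 but not stated.

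**Step 1: algebra.** Take logit P = a + b_g·Group_g + c·A, with A = 100 for every control. A does not vary in Group 1, so c is estimated only within Groups 2-4. Then, approximately,

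adjusted b_g ≈ unadjusted b_g + c × (100 − mean adherence in group g).

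On one simulated dataset the right-hand side gave −0.91, −0.37 and −0.17; the fitted coefficients were −0.94, −0.38 and −0.17.

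**Step 2: how far the assigned constant drives the result.** On another simulated dataset only the control value was changed. The slope stayed at −0.462 per 10 points. The Group 2 coefficient (unadjusted −0.55) was +3.19, +0.88, −0.73 and −1.43 with controls coded 0, 50, 85 and 100. The first step is 5 × −0.462 = −2.31, which takes +3.19 to +0.88; the others follow in the same way. So, for a given slope, the value assigned to controls sets the group coefficient.

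**Step 3: bias under a true null.** Assumed, not in the documents: adherence drawn with mean 80%, SD 20 and cut to 0-100 (realised mean 78%, SD 17); per-visit outcome rate 40%; woman random-effect SD 1 on the logit scale. Each scenario had 4,000 trials of 4 × 17 women with four visits, analysed by exchangeable logistic GEE with robust standard errors, two-sided 0.05. Without adherence the median OR is 1.00, with about 6% false positives per arm. With adherence:

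| Correlation of adherence with lower BV risk | Median OR | False positives per arm |
|---|---|---|
| 0.5 | 0.58 | 22% |
| 0.3 | 0.73 | 12% |
| 0 | about 1.0 | 6% |
| −0.3 | 1.37 | 12% |
| −0.5 | 1.70 | 21% |

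Varying the inputs (mean 90 with SD 12; SD 10; outcome rate 25%) gives ORs of 0.59-0.76 at correlation 0.3 and 1.31-1.74 at −0.3. Varying the random-effect SD from 0.5 to 1.5 gives about 0.84 to 0.67 at 0.3. With SD 1 and half of product users at 100% (mean 94%), the OR at 0.3 is 0.85. At correlation 0.1 in the base case it is 0.91.

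**Step 4: a second set of assumptions.** Mean adherence about 83%, SD about 15, 20% of users at 100%, between-woman SD 1.2, control rate about 50%, latent correlation ±0.6. With 20,000 women per group and no product effect, the adjusted log OR is −0.67 when lower-risk women adhere more (unadjusted −0.01). Step 1 predicts this: the slope is −0.39 per 10 points, so −0.01 + (−0.39 × 1.70) = −0.67. With the reverse relation it is +0.65 (unadjusted 0.00). At 17 per group, rejection is 29-30%, against about 6% without adherence.

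**Step 5: precision.** In a linear model the variance of b_g is proportional to 1/17 + 1/17 + (100 − mean)²/(48·SD²), where 48 = 3 × 16. The inflation is 1 + (17/96) × ((100 − mean)/SD)² = 1 + 0.177 × ((100 − mean)/SD)². At mean 78 and SD 17 this is 1 + 0.177 × (22/17)² = 1.30. The Step 3 simulation at zero correlation gave an SD of the log OR of 0.506 against 0.442, and (0.506/0.442)² = 1.31. From mean/SD 95/10 to 70/20, the standard error rises by 2% to 18%.

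**Step 6: ranking of products.** With equal mean adherence the order does not change. With realised arm means of 87%, 78% and 68% and correlation 0.3, three inert products show ORs of 0.82, 0.73 and 0.62. The least-used product looks best in 53% of trials instead of 33%. At −0.3 the ORs are 1.20, 1.36 and 1.61.

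**The case against.** The strongest defence is one of scope and target. This is a descriptive pilot, and the randomised comparison is already reported without adherence for five outcomes, three periods and five contrasts. If the GEE is read as a full-adherence analysis, 100% is a coherent value for women with no product to miss. With a pure dose effect and no link to prognosis, the coefficient does estimate that effect: in the Step 4 set-up it was −0.78, against −0.64 unadjusted. This limits the damage to two models. It does not rescue them as written, because SAP 6.4 presents adherence as confounding, names no such estimand, and offers no argument that adherence is unrelated to prognosis.

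Three narrower points stand as qualifications:

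- 100% is the bound of the scale, so the coefficient is a prediction at that bound. It is literal extrapolation only in a group where few women reach it.
- The precision loss is modest.
- The sizes are illustrative. The correlation, the adherence distribution and the between-woman SD are all assumed, and milder values give ORs nearer 1. Neither simulation includes the CT/NG term.

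It is also true that the SAP already contains attendance through M6 and CT/NG counts by group, so any change now comes after data collection and should be recorded as such.

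**Conclusion.** The concern holds and should be fixed. As specified, the adjusted group coefficients do not estimate the effect of randomised assignment; they estimate an undeclared, model-based contrast at full adherence. That follows from the coding and, to the stated approximation, from linear entry of adherence on the logit scale.

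The direction and size of the bias cannot be determined from the documents. Under the assumptions shown, a correlation of 0.3 in either direction moves a null OR to roughly 0.73 or 1.37 and doubles the false-positive rate to about 12%. If adherence is unrelated to BV risk there is no bias, only a standard error about 14% larger in the base case (0.506/0.442). The order of products is at risk only if mean adherence differs between arms. The intent-to-treat rate ratios remain valid as the randomised comparison.

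**What to change.** Remove adherence from the GEE models that compare randomised groups, and state that covariates in those models must be measured before randomisation. If a behavioural variable is added because of imbalance or change over time, use its baseline value.

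Keep the planned adherence plots. Any analysis relating adherence to outcome should be separate, confined to Groups 2-4, and labelled exploratory and non-randomised.

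The cost is a change to SAP 6.4, dated and noted as made after data collection, with no new data. The main GEE would no longer give a full-adherence estimate, but that estimate has no causal basis as specified.
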